### **7.1.5. Events That Do Not Meet the Definition of an SAE**

Elective hospitalizations to administer or to simplify trial treatment or trial procedures (e.g., overnight stay to facilitate chemotherapy and related hydration therapy application) are not

considered SAEs. However, all events leading to unplanned hospitalizations or unplanned prolongation of an elective hospitalization (e.g., undesirable effects of any administered treatment) must be documented and reported as SAEs.

#### **7.1.6. Events not to be Considered as AEs/SAEs**

Medical conditions present at the initial trial visit that do not worsen in severity or frequency during the trial are defined as baseline medical conditions, and are not to be considered AEs.

#### **7.1.7. AE/SAEs Observed in Association with Disease Progression**

Disease progression recorded in the course of efficacy assessments only, but without any adverse signs or symptoms, should not be reported as an AE. However, if adverse signs or symptoms occur in association with disease progression, these should be recorded as AEs and as SAEs if they meet any seriousness criteria.

#### **7.1.8. Predefined Potential AEs of Special Interest for Safety Monitoring**

Selected non-serious and SAEs defined below are considered AESIs and must be recorded as such on the Adverse Event case report forms/worksheets and reported within 24 hours to the Sponsor either by electronic media or paper. Sponsor Contact information can be found in the Investigator Trial File Binder (or equivalent).

Events of clinical interest for this trial include:

- Infusion-related reactions.
- An elevated AST or ALT lab value that is greater than or equal to 3X the upper limit of normal and an elevated total bilirubin lab value that is greater than or equal to 2X the upper limit of normal and, at the same time, an alkaline phosphatase lab value that is less than 2X the upper limit of normal, as determined by way of protocol-specified laboratory testing or unscheduled laboratory testing.

Note: These criteria are based upon available regulatory guidance documents. The purpose of the criteria is to specify a threshold of abnormal hepatic tests that may require an additional evaluation for an underlying etiology. The trial site guidance for assessment and follow up of these criteria can be found in [Section 5.6.4](#).

- Any AE that is reasonably suspected to be immune-mediated (ie, an irAE).

AESIs (both non-serious and serious AEs) identified in this guidance document from the date of first dose through 90 days following cessation of treatment, or 30 days after the initiation of a new anticancer therapy, whichever is earlier, need to be reported to the SPONSOR within 24 hours of the event, regardless of attribution to study treatment, consistent with standard SAE reporting guidelines and either by electronic media or paper.

Subjects should be assessed for possible AESIs prior to each dose. Lab results should be evaluated and subjects should be asked for signs and symptoms suggestive of an immune-related event. Subjects who develop an AE thought to be immune-related should have additional testing to rule out other etiologic causes. If lab results or symptoms indicate a possible irAE, then additional testing should be performed to rule out other etiologic causes. If no other cause is found, then it is assumed to be immune-related.

Any infusion reaction, regardless of Grade, must be reported in an expeditious manner and will be considered an AESI. The reporting of AESI is described in [Section 7.2.2](#).

## 7.2. Methods of Recording and Assessing Adverse Events

At each trial visit, the subject will be queried on changes in his/her condition. During the reporting period of the trial, any unfavorable changes in the subject's condition will be recorded as AEs, whether reported by the subject or observed by the investigator.

Complete, accurate, and consistent data on all AEs experienced for the duration of the reporting period (defined below) will be reported on an ongoing basis in the appropriate section of the eCRF. Among these AEs, all SAEs and all non-serious AESIs must be additionally documented and reported using the appropriate report form as described in Section 7.2.2.

It is important that each AE report include a description of the event, its duration (onset and resolution dates and times to be completed when it is important to assess time of AE onset relative to recorded treatment administration time), its severity, causal relationship with trial treatment, any other potential causal factors, any treatment administered or other action taken (including dose modification or discontinuation of study drug), and outcome. In addition, serious cases should be identified and the appropriate seriousness criteria documented.

Specific guidance can be found in the eCRF Completion and Monitoring Conventions.

### 7.2.1. Definition of the Adverse Event Reporting Period

The AE reporting period for safety surveillance begins when the subject provides written consent and continues until either 90 days after the last dose of study drug or the start of new anticancer treatment, whichever comes first. Following the End-of-Treatment Safety Follow-up Visit, only treatment-related AEs will be documented through the Treatment Follow-up Period of up to 12 months after the last dose of study drug or until disease progression and/or initiation of a new line of therapy, whichever comes first.

Any SAE suspected to be related to trial treatment must be reported whenever it occurs, irrespective of time elapsed since last dose of study drug.

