 Tumor tissue for biomarker analysis from a biopsy of a tumor lesion not previously irradiated must be available for PD-L1 expression and HPV evaluation. Only biopsies obtained at the time of or after the diagnosis of metastatic disease will be evaluated for PD-L1 expression. If a tumor biopsy was obtained from a target lesion during eligibility assessment, it is preferred to obtain a new baseline scan. Biopsy of lesions on study should be limited to non-target lesions or new lesions if their pathologic etiology is ambiguous. FOR SUBSEQUENT EVEN CYCLES: An **optional biopsy** is desired at Cycle 4 ONLY and, if provided, should be collected on Day 1 **before** AGEN2034 administration.

 Adverse events will be documented from time of consent up until 90 days after the last dose of study drug or the start of a new anticancer treatment, whichever comes first.

Following the End-of-Treatment Safety Follow-up Visit, only treatment-related AEs will be documented through the Treatment Follow-up Period of up to 12 months after the last dose of study drug or until disease progression and/or initiation of a new line of therapy.

 12-lead ECG on Cycle 1 Day 1, before AGEN2034 infusion starts and 2 hours (-10/+ 20 min) after infusion ends; on subsequent cycles as indicated 1 hour (-10 / + 20 min) after infusion ends or at visits indicated.

6a (At selected sites only) Expanded ECG Evaluation (triplicate tracings; see [Section 6.4.3.4](#)): 12-lead ECGs will be taken for Cycles 1 and 4 on Day 1 within 15 min ( $\pm$  10 min) before the Predose PK sample and within 15 min ( $\pm$  10 min) before the 30-min-after-end-of-infusion PK sample, and on Day 2 within 15 min ( $\pm$  10 min) before the 24-h-after-end-of-infusion PK sample. ECGs (12-lead, triplicate tracings) will also be taken for every subsequent 8th cycle for up to 1 year (approximately every 4 mo [in Cycles 12, 20, and 28]) on Day 1 within 15 min ( $\pm$  10 min) before the Predose PK sample and within 15 min ( $\pm$  10 min) before the 30-min-after-end-of-infusion PK sample.

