#### **6.3.3.2. Safety Follow-up Visit**

The mandatory Safety Follow-Up Visit should be conducted for all subjects approximately 4 weeks after the last dose of study drug or before the initiation of a new antineoplastic treatment, whichever comes first. Subjects with an AE of Grade >1 will be further followed until the resolution of the AE to Grade 0-1 or until beginning of a new antineoplastic therapy, whichever occurs first. Subjects with an adverse drug reaction (ADR) ongoing at the Safety Follow-up Visit must be followed up until the ADR resolves, becomes stable, or is considered not clinically significant by the investigator.

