### **7.3. Monitoring of Subjects with Adverse Events**

Adverse events are recorded and assessed continuously throughout the trial starting at the time the subject receives his/her first treatment ([Section 7.2.1](#)) and are assessed for final outcome at the end-of-treatment visit.

After the End-of-Treatment Safety Follow-up Visit, only treatment-related AEs will be documented through the Treatment Follow-up Period of up to 12 months after the last dose of study drug or until disease progression and/or initiation of a new line of therapy.

All SAEs ongoing at the post-treatment safety follow-up visit must be monitored and followed by the investigator until stabilization or until the outcome is known, unless the subject is documented as “lost to follow-up.”

Reasonable attempts to obtain this information must be made and documented. It is also the responsibility of the investigator to ensure that any necessary additional therapeutic measures and follow-up procedures are performed.

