5.3. DEFINITION OF ON-TREATMENT PERIOD

On-treatment period is defined as the time from the first dose of study treatment until the end of treatment safety follow-up (4 weeks \pm 7 days from the last dose of study drug, i.e., until 35 days from the last dose) or end of study, whichever occurs first.

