5.4. DEFINITION OF AN EXTENDED ON-TREATMENT PERIOD

Extended on-treatment period (follow-up) is defined as the time from the first dose of study treatment through 90 days after the last dose of study treatment or end of study, whichever occurs first. This is used for reporting immune-related AEs and also as a sensitivity analysis for reporting all treatment emergent adverse events.

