7.6.2. Adverse Events

Adverse events (AEs) will be coded using MedDRA v22.1 or later and will be classified by SOC and PT.

Severity of AEs will be assessed by investigators according to NCI-CTCAE v4.03, and AEs will be classified by the investigator as either related or not related to study drug

Pre-existing conditions are those that started before and continued after signing of informed consent. Prior AEs (non-treatment emergent) are those occurring after the subject signed the informed consent and before the administration of the first dose of study treatment. Immune-related AEs will be evaluated in the extended on-treatment period to account for late toxicities. A separate listing will be provided for AEs incurred after on-treatment period.

TEAEs are AEs with onset during or after administration of first dose, or the worsening of a pre-existing condition during the on-treatment period. Immune-related AEs will be considered TEAEs during the extended on-treatment period. In a sensitivity analysis, TEAEs will be defined as AEs with onset during or after administration of first dose, or the worsening of a pre-existing condition during the extended on-treatment period. A separate listing will be provided of all AEs with onset date, or worsening date between end of “On-treatment period” (35 days) and end of “Extended on-treatment period” (90 days).

Any missing onset date, causality, or severity must be queried for resolution. Unresolved / missing causality and severity will be handled according to the following rules:

- An unresolved causality will be considered treatment-related
- An unresolved severity will be identified as an unknown severity

AEs with partial dates will be considered TEAEs unless the AE can unequivocally be determined as not treatment emergent.

The following AEs are considered as AEs of special interest (AESIs):

- Infusion-related reactions per definition in NCI-CTCAE v4.03 specification (*per investigator assessment*)
- Lab-based hepatic toxicity: An elevated aspartate transaminase (AST) or alanine transaminase (ALT) lab value \geq to $3 \times$ upper limit of normal (ULN) with a corresponding elevated total bilirubin value $\geq 2 \times$ ULN, at the same time, an alkaline phosphatase lab value $< 2 \times$ ULN, as determined by way of protocol-specified laboratory testing or unscheduled laboratory testing
- Any AE suspected to be immune-mediated (i.e. an irAE) by the investigator

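### The protocol gives two conflicting rules for recording unrelated adverse events between the safety follow-up visit and day 90, and the SAP's 90-day safety outputs assume the fuller one

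*Protocol*

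**What the plan says.** **Protocol, fuller rule.** Section 7.2.1 starts AE reporting at consent and "continues until either 90 days after the last dose of study drug or the start of new anticancer treatment, whichever comes first". Footnote 5 of Table 13, the Phase 2 schedule, opens in the same way: "Adverse events will be documented from time of consent up until 90 days after the last dose of study drug". Neither sentence limits recording by relatedness.

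**Protocol, restrictive rule.** The next sentence of 7.2.1 reads "Following the End-of-Treatment Safety Follow-up Visit, only treatment-related AEs will be documented through the Treatment Follow-up Period", with an outer limit of 12 months or progression or new therapy. Footnote 5 goes on in the same words. Section 7.3 has no 90-day sentence and gives only this rule: "After the End-of-Treatment Safety Follow-up Visit, only treatment-related AEs will be documented through the Treatment Follow-up Period". Section 6.3.3.2 places the visit "approximately 4 weeks after the last dose of study drug or before the initiation of a new antineoplastic treatment, whichever comes first".

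**Events covered under either rule.** Section 7.2.2.1 requires any new SAE in the reporting period to be reported, whatever its attribution. Section 7.1.8 requires AESIs to be reported, also whatever the attribution, to 90 days after treatment ends or 30 days after new anticancer therapy, if that is earlier.

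**SAP.** The main on-treatment period (5.3) runs "until 35 days from the last dose". The extended period (5.4) runs to day 90 or end of study. It serves immune-related AEs and "also as a sensitivity analysis for reporting all treatment emergent adverse events". Section 7.6.2 repeats this ("In a sensitivity analysis, TEAEs will be defined as AEs with onset during or after administration of first dose", or with worsening in the extended period). It adds a listing of all AEs between days 35 and 90, and reports immune-mediated clusters over the extended period. The clusters are defined by MedDRA preferred term, with no filter on investigator attribution. None of these outputs carries a caveat about how completely late events were recorded.

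**The concern.** An all-cause AE analysis to day 90 is sound only if all-cause AEs were recorded to day 90. The protocol can be read either way, so one site may have followed one rule and another site the other.

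This is an open-label, single-arm trial, so relatedness is judged by investigators who know the treatment and there is no control arm. If late recording depends on that judgement, a late event that nobody yet suspects is the kind most likely to be left out. The clusters are exposed too. A non-serious diarrhoea or rash on day 50 that is judged unrelated and not immune-mediated would belong in its cluster by preferred term, but under the restrictive rule it need not be recorded. A low late count in these tables could then reflect the recording rule and not the drug.

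**Working it through.** The plan states no figure for this point. Its one safety sizing figure, at least 77% probability of seeing an AE with a 1% rate in 150 subjects, reproduces (1 − 0.99^150 = 0.7785) and is not affected. The check is a comparison of time windows.

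**Inputs**
- Safety visit day v after last dose: 28 nominal, 21 to 35 allowed (Table 13 window; SAP 5.3).
- End of main on-treatment window: 28 + 7 = day 35 (SAP 5.3).
- End of extended window: day 90 (SAP 5.4).
- End of all-AE reporting under the fuller rule: day 90 or new anticancer treatment (Protocol 7.2.1).

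**Length of the disputed period** = 90 − v. **Part of it inside the main window** = 35 − v.

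| Visit day v | 90 − v | 35 − v |
|---|---|---|
| 21 | 69 days | 14 days |
| 28 | 62 days | 7 days |
| 35 | 55 days | 0 days |

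**Which events are exposed under the restrictive rule.** Related AEs are still recorded under that sentence until its own stopping events, new SAEs under 7.2.2.1 and AESIs under 7.1.8. The remainder is unrelated, non-serious and not an AESI.

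**Share of late events lost.** Let u be the share of post-visit events that are of this kind. The loss is u under the restrictive rule, and the relatedness limit causes none under the fuller rule. The documents give no value for u. Assumed values from 0.2 to 0.8 simply mean a loss of 20% to 80% of late events. This range is illustrative and is not an estimate.

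**New anticancer treatment.** Under either rule, all-AE collection stops when new treatment starts, on day s after last dose, while the SAP window continues. The uncollected part of the SAP window is 90 − s days. As an assumed example, s = 28 leaves 90 − 28 = 62 days. AESI reporting would extend to day 28 + 30 = 58, leaving 90 − 58 = 32 days without it. The protocol's own on-treatment period (8.3.4) ends the day before new anticancer therapy; the SAP's two periods have no such cut.

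**The case against.** The best defence is that the fuller rule governs. Section 7.2 asks for complete data on all AEs throughout the reporting period, and 7.2.1 defines that period as 90 days. Table 13 schedules AE review at the 3-month visit, which every subject who discontinues is to attend. On this reading the related-only sentence matters only from day 90 to month 12, and the relatedness limit loses nothing. Section 7.2 also points to eCRF conventions that are not available here and may settle the matter.

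This defence has force, and it rules out one tempting inference: that the 90-day analysis must undercount by design. That follows only if the restrictive sentence was applied. The defence does not remove the conflict, because that sentence takes effect at the visit and stands alone in 7.3.

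Three other stronger readings are not supported.
- A reader might infer that only AESIs and related SAEs are kept after the visit. Section 7.2.2.1 contradicts this: unrelated SAEs are also required during the reporting period.
- A reader might add that most subjects stop for progression, so that even related recording has ended for them. The progression limit does appear in the restrictive sentence. The 90-day period itself ends early only for new anticancer treatment, though, and the documents give no discontinuation counts.
- A reader might express the gap as a share of follow-up. For an assumed 6 doses, the time from first dose to day 90 after the last is 14 × 5 + 1 + 90 = 161 days, and 55/161 = 34%. For 12 doses it is 14 × 11 + 1 + 90 = 245 days, and 55/245 = 22%. These are shares of calendar time, count only from day 35, and say nothing about the share of events missed.

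It is also fair to say that the 90-day all-TEAE analysis is a sensitivity analysis, and that investigator-suspected immune-related events are protected as AESIs. In addition, a not-related call needs a reasonable alternative explanation (Protocol 7.1.1), and unresolved causality counts as related (SAP 7.6.2). These points limit the harm. They do not protect the preferred-term clusters, which include events the investigator did not think immune-mediated.

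**Conclusion.** The protocol contradicts itself on what is recorded between the safety visit and day 90, and the SAP builds three sets of outputs on that period without noting it. If the restrictive rule is followed, capture of unrelated, non-serious, non-AESI events is missing for 55 to 69 days (62 at the nominal visit). At most 14 of those days fall inside the main 35-day window. The day ranges assume that the visit falls within its stated window.

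The number of events lost is unknown. If the fuller rule is followed, the only loss is after new anticancer treatment, where SAP and protocol still disagree. The primary endpoint and the stated power figures are unaffected. The point concerns the completeness and labelling of late safety data.

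**What to change.** **Protocol.** Reconcile 7.2.1, 7.3 and footnote 5 of Table 13. Record all AEs, whatever their attribution, to 90 days after the last dose or the start of new anticancer treatment, and only related AEs after that to 12 months.

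**If the restrictive rule was already applied.** The SAP sets a data cutoff of 11 Feb 2021, so much of the collection may be past changing. In that case, state in the SAP and the study report which rule the eCRF applied. Then either restrict the outputs from the visit to day 90, including the clusters, to related AEs, all SAEs and AESIs, or keep them and label them incomplete for unrelated non-serious events. A restriction to related AEs and AESIs alone would discard unrelated SAEs that the protocol requires, so SAEs must stay in.

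**In either case.** Align the SAP windows with the stop of collection at new anticancer treatment.

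**Cost.** Slightly more AE recording between weeks 4 and 13, for which a 3-month visit with AE review already exists. Otherwise, a few sentences in the SAP and a caveat on the late-safety tables.

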### 7.2.2. Procedure for Reporting SAEs / AESIs

All adverse reactions will be reported to the FDA according to 21 Code of Federal Regulations (CFR) 312.32 and according to applicable regulatory authorities and institutional ethics committees.

#### 7.2.2.1. Serious Adverse Events

In the event of any new SAE (of any Grade) occurring during the reporting period, the investigator must immediately (i.e.,  $\leq$  24 hours after becoming aware of the event) inform the Sponsor or designee by telephone, fax, or e-mail. For the following significant SAEs the reporting period to the Sponsor is  $\leq$  8 hours after becoming aware of the event:

- Drug-related death less than 30 days of dosing
- Drug-related life-threatening event.

When an event (or follow-up information) is reported by telephone, a written report must be sent immediately thereafter by fax or e-mail.

Reporting procedures and timelines are the same for any new information on a previously reported SAE (= follow-up).

For names, addresses, telephone, and fax numbers for SAE reporting, see information included on the SAE report form.

All written reports should be transmitted using the SAE report form, which must be completed by the investigator following specific completion instructions. The AE section of the eCRF must be completed. Relevant pages from the eCRF may be provided in parallel (e.g., medical history, concomitant drugs).

In all cases, information provided in the SAE report form must be consistent with data on the event that is recorded in the corresponding eCRF sections.

The investigator/reporter must respond to any request for follow-up information (e.g., additional information, outcome and final evaluation, specific records where needed) or to any question the Sponsor or designee may have regarding the AE within the same timelines as described for initial reports. This is necessary to permit a prompt assessment of the event by the Sponsor or designee and (as applicable) to allow the company to meet strict regulatory timelines associated with expedited safety reporting obligations.

Requests for follow-up will usually be made by the responsible monitor, although in exceptional circumstances the Sponsor's global drug safety department may contact the investigator directly to obtain clarification or to discuss a particularly critical event.

